Other outcomes to explore in the current study include preparation quality and PDR. Yoo et al⁸ reported that 99% of patients receiving PEG+SIM had BPS scores of 6-9 compared to only 84% in the patients who received PEG. Considering BPS scores as the outcome (p1=99% and q1=84%), with $\alpha=0.05$ and $\beta=0.2$, a total of 110 patients will be needed, 55 in each arm. On the other hand, Jansen et al⁹ reported that PDR in patients who received PEG+SIM was 26.7% compared to 13.7% in those who received PEG. With these results and following the same formula, a sample size of 150 patients per group will be needed to evaluate both bowel preparation and PDR. Therefore, in order to have a sufficient study power and examine all parameters (ADR, PDR and bowel preparation quality), we decided to include 150 patients per group for a total of 300 patients.

Statistical analysis

1. Continuous data (e.g. effective procedure time, withdrawal time) will be described using mean and standard deviation (SD) or Median (Q1, Q3) based on D'Agostino-Pearson normality test in each group and will be compared with either independent t-test or nonparametric Mann-Whitney. Interval data (e.g. BPS, BS) will be presented as Median (Q1, Q3) in each group and compared with nonparametric Mann-Whitney. Categorical data (e.g. ADR) will be described using frequency and proportion (%) in each group and will be compared using Chi-square or Fisher's exact test where appropriate. Further, number needed to treat (NNT) using SIM+PEG will be determined. Cohen's kappa coefficient will be used to measure inter-rater agreement between two endoscopists who will score BS and BPS. In the eventual presence of baseline differences in cofactors, a relative risk regression developed by our biostatistician¹⁴ will be used

to determine adjusted effect of SIM+PEG compared to PEG alone on PDR and ADR. Other findings at colonoscopy

All the statistical analyses will be performed using STATA 14 and p-values less than 5% will be considered significant results. All the statistical analyses will be performed by our Biostatistics and Epidemiology Consulting Lab (BECL) under the supervision of [name].

METHODS

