Colonoscopies will be performed by 4 experienced endoscopists who will be blind to the type of preparation the patient received. All procedures will be performed using Olympus 190 colonoscopes. During colonoscopy, standard parameters such as cecal intubation time, withdrawal time and number of polyps detected will be recorded. For the purpose of this study, withdrawal time will be measured as follows: the timer will be started upon initiation of endoscope withdrawal once the cecum has been reached, and it will be paused every time the endoscopist needs to perform any maneuver or intervention such as polypectomy, biopsy, clip placement, hemostasis, suction for >5 seconds etc. Once the endoscopist is done performing any of these, the timer will be re-started. Endoscopists will be free to ask for SIM during the procedure if he/she deems it necessary and the amount will be recorded by the research coordinator. In addition, endoscopists will be asked to score the preparation according to

the standardized BS (0-3; 3 being the worst) and the BPS (3-0; 3 being the best) . A total BPS score of >6 and a BS of <2 will be considered adequate preparations.

The BS that will be used in this study is the one previously used by Sudduth et al (7). This score grades different sections of the colon as follows: 0 = no or minimal, scattered bubbles believed not to be interfering with the examination; 1 = bubbles covering at least half the luminal diameter; 2 = bubbles covering the circumference of the lumen; 3 = bubbles filling the entire lumen. The overall BS and BPS scores will be determined by adding the scores of each segment of the colon (rectosigmoid, transverse and ascending). For example, in a patient whose individual segment BS scores are as follows: 0,2,1; the final score is 3. All endoscopists will be trained in the use of both scales prior to their participation in the study. The bubble scale and the BPS scores will be independently determined by the endoscopist performing the procedure and by a second endoscopist who will review the still previously selected and labeled by the performing endoscopist and will assign his own score based on these images. Each endoscopist will be blind to the score provided by the other one and inter-observer agreement will be calculated.

The ADR will be calculated once the pathology results of the polyps removed become available.

INNOVATIONS

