To the best of our knowledge, this is the first study designed specifically to evaluate the effect of high dose of SIM in conjunction with 4 L PEG preparation on ADR in a western population. Our pilot design will produce rapidly available data that will be then used to design a full sized trial that will definitively confirm or refute our hypothesis, which is that adding SIM to PEG improves ADR. Our study is innovative in its methodology in the following aspects: 1. It is the first one to use a 4 L PEG preparation in both arms (previous studies have used 2 L PEG or other CPAs); 2. It is the first one performed in a standardized average risk western population undergoing screening colonoscopy (previous studies have included both screening and diagnostic colonoscopies); 3. It is a randomized controlled trial and its proposed methodology is a cost-effective approach compared to other alternatives; and 4. Inter-observer agreement of both BPS and BS will be calculated, reducing the potential for bias.

REFERENCES

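### Agreement on BS and BPS is conditional on stills the first rater chose, so kappa cannot show independent reproducibility or support the claim that it reduces bias

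*Combined protocol and SAP*

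**What the plan says.** In the combined protocol and SAP, METHODS describes two scorings of each preparation. On the first it says: "The bubble scale and the BPS scores will be independently determined by the endoscopist performing the procedure". The other scorer is "a second endoscopist who will review the still previously selected and labeled by the performing endoscopist", who "will assign his own score based on these images". The safeguard offered is: "Each endoscopist will be blind to the score provided by the other one and inter-observer agreement will be calculated". Separately, the performing endoscopists are blinded to arm: "Colonoscopies will be performed by 4 experienced endoscopists who will be blind to the type of preparation the patient received".

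The Statistical analysis section names the statistic: "Cohen's kappa coefficient will be used to measure inter-rater agreement between two endoscopists who will score BS and BPS". It gives no weighting, no scoring level (segment or three-segment total), no target value and no confidence interval.

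INNOVATIONS lists as a strength: "Inter-observer agreement of both BPS and BS will be calculated, reducing the potential for bias".

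The documents do not say how many stills are taken or from where, what the label may contain, or whether the second reader is blind to arm. They also do not say whether the stills come before or after washing, suction or SIM given during the procedure, or at what point the performing endoscopist scores.

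**The concern.** Two ratings are independent assessments of a colon only if each rater's view of it does not pass through the other's judgement. Here the first rater's choice of pictures is the second rater's only evidence. Blinding to the number stops direct copying, but the choice of pictures can still convey an impression. A dirty or bubbly stretch that was overlooked or not photographed cannot be found by the second reader.

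Kappa is the only planned check on the reliability of BS and BPS. Preparation quality is a secondary endpoint, and BPS has its own sample-size calculation. INNOVATIONS also says the pilot will inform a full-sized trial. A reliability figure that cannot be interpreted would carry forward into that design, together with the claim that it reduced bias.

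**Working it through.** **1. The plan's own figure.** There is none to reproduce. No kappa, target agreement or reliability sample size is stated. The per-group sizes of 509, 55 and 150 are for ADR, BPS and polyp detection comparisons between arms and do not bear on agreement.

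**2. The statements side by side.**

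- The first score comes from the procedure; the second comes only from images the first rater picked and labeled.
- The scores are called independent, but the second is conditional on the first rater's selection.
- Mutual score-blinding removes one path (seeing the number) and leaves the other (the choice of images).
- Calculating agreement measures reliability. It changes no score and so cannot by itself reduce bias. Protection against arm-related bias comes from blinding to preparation.

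**3. Can the direction of distortion be known?** I checked this by simulation. All inputs are assumptions, because the documents give none beyond three segments scored 0 to 3.

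- 20,000 patients; true segment level μ normal with mean 2.0, SD 0.8, in the BPS direction (3 best).
- 30 views per segment, each μ plus view-to-view variation of SD 0.8.
- First score = round(mean of all 30 views + error), limited to 0–3.
- Second score = round(mean of the views shown + error), limited to 0–3.
- Error SD 0.3, 0.4 or 0.6 for both raters; two stills per segment when stills are used.
- κ = (p_o − p_e)/(1 − p_e), unweighted, at segment level.

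| Second rater sees | SD 0.3 | SD 0.4 | SD 0.6 |
|---|---|---|---|
| Full examination | 0.56 | 0.44 | 0.28 |
| Two random stills | 0.36 | 0.30 | 0.22 |
| Two stills closest to first score | 0.88 | 0.74 | 0.53 |
| Two cleanest | 0.00 | 0.03 | 0.06 |
| Two worst | −0.09 | −0.06 | 0.01 |

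Reading the SD 0.4 column:

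- Loss of information alone (random stills against full view): 0.30 − 0.44 = −0.14.
- Selection with the number of stills held at two: matching 0.74 − 0.30 = +0.44; cleanest 0.03 − 0.30 = −0.27; worst −0.06 − 0.30 = −0.36.

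**4. Does the form of kappa matter?** At SD 0.4, quadratic-weighted segment kappa was 0.71 (full), 0.60 (random), 0.88 (matching), 0.22 (cleanest) and 0.28 (worst). The ordering of full, random and matching is unchanged, and cleanest and worst remain far below them. The gain from matching over full view is smaller: 0.88 − 0.71 = 0.17, against 0.74 − 0.44 = 0.30 unweighted.

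The sign therefore depends on how the stills are chosen. The size also depends on the assumed variances and on the form of kappa, and the plan fixes none of these.

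**The case against.** A reader might infer that the design inflates kappa with certainty. The documents do not support that. METHODS states no selection rule, and inflation follows only if stills are picked to match the first rater's impression. Picking the cleanest or worst views lowers kappa in the illustration, and so does comparing a live examination with a few stills.

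A reader might also infer that the first rater already knows his own score when choosing. The text says only that selection comes before the second reader's review; it does not place scoring before selection.

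Nor would every error by the performing endoscopist go unnoticed. A second reader who applies the scale differently to the same picture will disagree, and kappa will show it. Only errors about mucosa not shown are hidden. The endoscopists are trained on both scales beforehand.

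The strongest objection concerns materiality. Kappa enters no between-arm test, sample-size calculation or decision rule. ADR rests on pathology, the performing endoscopists are blind to preparation, and patients are told not to disclose their regimen.

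All of this stands, and it limits the point. It does not rescue the description of the scores as independent or the bias claim under INNOVATIONS. A reliability figure with distortion of unknown sign is still not evidence of independent reproducibility.

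**Conclusion.** The concern holds in a limited form. As planned, kappa is agreement conditional on images the first rater chose. It may be raised or lowered, it is blind to errors about mucosa outside the stills, and it does not support the statement that bias is reduced. This follows from the text and needs no numerical assumption.

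The size and direction cannot be determined from the documents. The simulated kappas illustrate the possible mechanisms and are not estimates for this trial; the matching, cleanest-only and worst-only rules are deliberate extremes.

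The consequence is confined to the reliability figure for a secondary outcome. Nothing here calls the ADR comparison or any other between-arm test into question. This is a cheap improvement, not a threat to the trial.

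**What to change.** In METHODS, replace free selection with a capture rule:

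- A set number of stills at named landmarks in each of the three segments.
- Capture at the same point relative to washing and intra-procedure SIM as the state the performing endoscopist scores. The protocol must therefore say what that state is; otherwise a timing mismatch would itself create disagreement.
- All stills kept, none selected.
- Labels limited to study code and segment or landmark.

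In INNOVATIONS, say that agreement on standardized stills will be reported, and delete the words about bias. While editing, state whether the second reader is blind to arm, and give the form of kappa (weighting and scoring level) with a confidence interval.

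The cost is a few sentences of text and a few seconds per procedure, with the same second reader, no video and no added staff. The resulting kappa may look less favourable. The rule cannot be applied to completed procedures, so it should be in place before enrollment.
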